We will also **include patients in the study who are starting an antidepressant medication** as this is the de facto treatment nationally in VA primary care settings for depression and also for our three study sites, with 70% of VA patients with new episodes of depression filling at least one antidepressant prescription. (See section E.6.a.) Prior studies of Beating the Blues (BTB) indicate there is no interaction between cCBT program use and either antidepressant treatment or depression severity. Benefits from the BTB and antidepressant medication have been additive. (35) However, we will consider whether a patient has filled an antidepressant prescription in our randomization scheme.

Exclusion criteria for the study will be narrow and include: 1) a diagnosis of schizophrenia, schizoaffective disorder, MDD with psychotic features, or Bipolar I in the past 12 months; 2) a positive screen for moderate or severe substance use in the past 6 months (per DSM 5); or 3) an immediate risk of suicide, requiring hospitalization or urgent evaluation (as evidenced by suicidal plan or intent).

Figure 3: Patient Identification and Screening

E.4 Patient Recruitment

Pharmacy data, patient diagnoses and CPT codes from outpatient visits are updated nightly from VISTA to the Corporate Data Warehouse (CDW), and study analysts have extensive experience in using these data. We will use these administrative data for preliminary identification of patients who may have new diagnoses of depression made in primary care. As in our pilot work, at this preliminary stage we will identify patients who may have new episodes of depression in primary care as those with at least two diagnoses of depression or one depression diagnosis accompanied by an antidepressant fill within 120 days of the diagnosis and *no prior depression diagnoses or antidepressant fills within 120 days* of the index date of their depression diagnosis. Patients must also have no diagnoses of schizophrenia, schizoaffective disorders, Bipolar I disorder, or major depression with psychosis in the prior year.

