At the time of our first in-person patient contact, we will begin our efforts to *retain* enrolled patients. During the initial assessment, patients will be asked to supply the names, phone numbers, and addresses of at least two family members, friends, or acquaintances—and give consent for staff to contact these individuals should we lose touch with the patient. As noted below, for the first 12 weeks, patients in the control condition will be receiving bi-weekly mailings giving depression self-management tips and patients in the PS-cCBT condition will be receiving peer specialist calls. These regular contacts will help maintain patients’ connection to the study. We will also send an additional mailing with study updates and logos to all patients at 18 weeks to help maintain a connection to the study and increase willingness to complete the final assessment. When needed, research staff will also check patient appointments and admissions to meet directly with patients near their scheduled assessment times.

We note that with similar procedures, we have been able to maintain a follow rate of $>85\%$ in prior RCTs even over longer time frames.

E.5 Patient Randomization

Eligible patients will be randomized to either enhanced PS-cCBT or to EUC. Random assignment will be coordinated and completed centrally at the study coordinating site to ensure that the RAs and clinical staff will not be able to determine the likely treatment assignment for the next enrollee. Randomization will be stratified by study sites, and to increase balance in prognostic factors between groups, minimization will be used for

randomization within each site. Factors to be included in minimization will include: 1) age group (≥ 55 vs. < 55), 2) gender, 3) antidepressant medication fill in prior 90 days vs. not, and 4) depression severity (PHQ-9 ≥ 15 vs. < 15) at time of baseline measures. Minimization method allows balancing on multiple factors, and we will utilize MinimPy, a free open-source, desktop minimization randomization program in this study.(61)(62)(63)

E.6 Study Groups and Intervention Description

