We also could have compared PC-cCBT or cCBT alone to **traditional in-person therapy**; however, other comparisons were of more pragmatic interest. Even if traditional in-person therapy has larger effect sizes, it is expensive and logically complex to deliver. Also, despite enormous efforts to bolster the capacity to deliver traditional in-person therapy, a small minority of Veterans with depression currently complete an adequate treatment trial. Thus, we were more interested in comparing a highly flexible treatment option (PS-cCBT) to usual care. PS-cCBT includes both basic psychotherapeutic content and a supportive relationship, and it may address issues that are currently barriers to completing in-person evidence-based psychotherapies, including therapist supply, travel difficulties, and patient time constraints.

Finally, we chose **not to restrict treatment options in usual care**, for example, by prohibiting antidepressant treatment, care management, or other psychotherapy. This decision was based on the ethical consideration of not depriving patients of any effective treatments that they might receive under naturalistic conditions. (Antidepressant medication is the default treatment in VA primary care, with 70% of patients with new diagnoses of depression receiving an antidepressant fill.) As prior studies of cCBT have shown no interactive effect of antidepressant treatment on cCBT effectiveness, study findings are likely to remain easily interpretable. We note that we deliberately consider antidepressant use in our randomization/minimization scheme. We also note that few individuals with new diagnoses of depression in primary care currently receive any definitive trial of psychotherapy.

As recommended when using enhanced usual care as a control group, we will carefully track and describe all care that patients receive during the study period.

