E.11.a Analyses of Success of Randomization: We will first determine the success of the randomization process for potential prognostic factors that may affect the primary outcomes of severity of depressive symptoms and functional status, but were not considered in minimization scheme. These factors include variables such as prior hospitalization or baseline severity of anxiety symptoms. Potential differences between groups will be determined through the use of t-tests or chi-square analyses, as appropriate. When there are significant differences in the distribution of these variables, they will be included as covariates in multivariable analyses. The interpretations of final results will also be made carefully in the presence of significant baseline differences.

E.11.b Analyses Relevant to Primary Aims: Primary study analyses will determine the effectiveness of the PS-cCBT intervention in decreasing depressive symptoms (IDS-SR), improving functioning and quality of life (VR-12, Q-LESQ-SF), and increasing recovery focus (RAS) at 24 weeks post-enrollment. We will also examine the impact of the intervention on depression coping efficacy and skills, antidepressant adherence, and initiation and completion of traditional in-person psychotherapy (contingent on symptoms).

Analyses will be of two broad types, those that assess intervention effects at each assessment point (12 weeks and 24 weeks), and those that determine effects over time. Primary analysis will be based on “intent to treat” principle, with all randomized patients included in the originally randomized group, regardless of whether they have subsequently dropped from their assigned treatment group.

Univariate Analyses: In the first phase of analysis (data verification), we will examine the distribution of all study variables to assess extreme values, missing data, variances, possible coding errors, skewness and whether or how to categorize skewed data. We will then describe means ($\pm SD$) for the continuous IDS-SR, VR-12, Q-LESQ-SF, and RAS measures by study group for each assessment time for the entire sample and

for each of the study sites, separately.

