Bivariate/Multivariate Analyses: We will evaluate bivariate associations between patients' treatment condition (PS-cCBT versus EUC) and the study outcomes to determine unadjusted measures of effect. We will also examine bivariate relationships between each of the potential covariates and the outcomes, and between each of the potential covariates and intervention group to assess possible confounders. Bivariate relationships between potential covariates will also be assessed for any collinearity in subsequent analyses.

Independent (Predictor) Variables	Dependent (Outcome) Variables
Treatment Group PS-cCBT vs Usual Care Potential Covariates Demographics Baseline measures of outcome variables Psychiatric comorbidities Study Site Social Support Prior to Enrollment General Primary Care Clinician Level of Depression Treatment Activity Distance to nearest VA facility	Primary Outcome Variables IDS-SR VR-12 Q-LES-Q-SF RAS Secondary Outcomes * Depression Coping skills (DCSES, CBTSQ) Antidepressant adherence Traditional psychotherapy use (contingent on symptoms) Hope Patient activation Anxiety Suicidal Ideation

* please note some secondary outcomes may be considered mediators in other study analyses

Effects At Each Assessment Time: Comparison at 24 weeks post-enrollment will be our primary comparison, but we will also assess patient outcomes to acute effects of the PS-cCBT intervention at 12 weeks. We will first obtain unadjusted differences in the outcomes between the two study groups with its associated 95% confidence interval. Comparisons of primary outcomes (IDS-SR, VR-12, Q-LES-Q-SF, RAS) between treatment groups at each assessment time will be accomplished using multiple regression models. Multiple regression models for each outcome variables will include the baseline values of the outcome variable as covariates to adjust for baseline differences, making the model analogous to analysis of covariance. We will also include two dummy variables for three sites and adjust for additional baseline covariates that show baseline imbalances in bivariate analyses.

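### The primary 24-week regression does not name the four minimization factors as covariates, and its imbalance-based selection rule will almost never admit them (low severity, a free improvement)

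*Combined protocol and SAP*

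**What the plan says.** **Randomization (E.5).** Allocation is stratified by site, and within site "to increase balance in prognostic factors between groups, minimization will be used". The factors are age group (cut at 55), gender, "3) antidepressant medication fill in prior 90 days vs. not, and 4) depression severity" (PHQ-9 cut at 15).

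**Primary regression (E.11.b, Effects At Each Assessment Time).** Week 24 is the primary comparison. The plan starts without adjustment: "We will first obtain unadjusted differences in the outcomes between the two study groups with its associated 95% confidence interval". The regression for each primary outcome then holds treatment, the baseline value of that outcome and site, after which: "We will also include two dummy variables for three sites and adjust for additional baseline covariates that show baseline imbalances in bivariate analyses".

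**Randomization check (E.11.a).** The check covers prognostic variables that might affect the primary outcomes "but were not considered in minimization scheme". The consequence of a positive test is: "When there are significant differences in the distribution of these variables, they will be included as covariates in multivariable analyses". No significance level is given.

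**Other routes into the model.** E.12 adds covariates found to predict missingness. E.9.d says that provider depression-care activity and psychiatric comorbidities go into study analyses, whereas the E.11.b table lists both only as potential covariates. That table names neither prior antidepressant fill nor PHQ-9 category; age and gender could come in under demographics.

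**The concern.** Minimization makes the arms more alike on the chosen factors than simple randomization would. When those factors predict outcome, the treatment estimate varies less from trial to trial. A model that omits them still leaves their contribution in the residual variance, so its standard error does not reflect the balance that the design achieved. Intervals come out somewhat too wide and the test somewhat conservative.

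The selection rule cannot repair this. It admits only covariates that look imbalanced, and minimization exists to prevent imbalance on these four. Site, the stratification factor, is already fixed in the model; the minimization factors are not treated the same way.

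A second consequence is that the adjusted primary model is not known until the baseline data have been tested by arm.

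**Working it through.** **1. The plan's own sample size (E.13).** Inputs: 0.4 SD, two-sided alpha .05, 90% power, 20% dropout.

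n per arm = 2(1.960 + 1.282)² / 0.4² = 131.3, so 132; 132 / 0.80 = 165 per arm, 330 in total. The plan's figure is reproduced. Power with 132 per arm is Φ(0.4·√66 − 1.96) = Φ(1.29) = 90.1% (89.9% with the t distribution).

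**2. Can the imbalance rule select the factors?** E.11.a excludes all four by its own terms. For the E.11.b rule, trials of 330 patients at three sites were simulated with minimization within site. The assignment probability is not in the documents and was varied.

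- Simple randomization, test level .05: at least one of the four factors is flagged in 18% of trials.
- Minimization with probability 1.0 / 0.9 / 0.8 / 0.7: 0 / 0 / 0.03 / 0.18% (up to 4,000 trials each).
- A larger run at probability 0.8 (200,000 trials): 0.001% at level .05 and 0.007% at .10.
- Age or PHQ-9 tested as a continuous score: roughly 0.1 to 0.7% each.

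**3. Cost of leaving them out.** Let R² be the share of outcome variance that the four factors explain beyond baseline outcome and site. With near-perfect balance the ratio of planned to adjusted standard error is about 1/√(1 − R²), times 0.998 for the extra parameters:

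0.998/√0.98 = 1.008; 0.998/√0.95 = 1.024; 0.998/√0.90 = 1.052; 0.998/√0.80 = 1.116.

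The 200,000-trial simulation (probability 0.8, 20% random dropout, 264 analysed) gives the same ratios. Prevalences were 20% women (prior-trial recruitment, E.2), 70% with a fill, and 50% for each of the age and PHQ-9 splits. ρ is the assumed baseline–outcome correlation.

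| Assumed R² | SE planned / adjusted | Null rejection, planned | Power at 0.4 SD, ρ = 0: planned vs adjusted | Power, ρ = 0.5: planned vs adjusted |
|---|---|---|---|---|
| 0 | 0.998 | .050 | 89.7 vs 89.6% | 96.1 vs 96.1% |
| .02 | 1.008 | .048 | 89.9 vs 90.1% | 96.2 vs 96.4% |
| .05 | 1.024 | .046 | 90.1 vs 90.9% | 96.4 vs 96.8% |
| .10 | 1.052 | .042 | 90.6 vs 92.4% | 96.6 vs 97.5% |
| .20 | 1.116 | .034 | 91.4 vs 94.9% | 97.1 vs 98.6% |

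The adjusted model rejects at .050 throughout (Monte Carlo SE .0005).

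Cross-check on the planned alpha, letting dropout remove a fifth of the balance: 2[1 − Φ(1.96/√(1 − 0.8R²))] = .048 / .045 / .041 / .032 for R² = .02 / .05 / .10 / .20, in line with the table.

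A smaller separate simulation (probability 0.9, 4,000 null trials per setting, Monte Carlo SE about .0035) gave .045 / .048 / .034 at R² .05 / .10 / .20, so there the conservatism is clear only at .20. At R² .02 it gave .061 for both models, a level that the larger run does not bear out.

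**4. What these R² values mean.** With an equal shift per factor, shift = √(R² / Σp(1 − p)), and Σp(1 − p) = .25 + .16 + .21 + .25 = .87. R² of .02 / .05 / .10 / .20 then needs each factor to move the outcome by 0.15 / 0.24 / 0.34 / 0.48 residual SD. If PHQ-9 category adds nothing beyond baseline outcome, the sum is .62 and age, gender and fill must each carry 0.18 / 0.28 / 0.40 / 0.57.

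**The case against.** **The effect is small.** This stands. Planned power is 89.7% or more in every row, so the 90% target is in effect met. The larger gains need R² of .10 to .20, which nothing in the documents supports.

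**Baseline IDS-SR already does the work of PHQ-9 severity.** This largely stands for IDS-SR, the outcome that the trial is powered on: a continuous baseline score of the same construct says more than a cut at 15. It is weaker for VR-12, Q-LES-Q-SF and RAS, and baseline IDS-SR does not directly capture age, gender or antidepressant fill.

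**A factor might still enter through E.12.** It might, if it predicts missingness, but the plan does not commit to that.

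**Stronger readings that the documents do not support.**

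- A reader might infer that the omission biases the estimate, inflates type I error or leaves the trial underpowered. The calculations show none of these.
- A reader might infer that testing for imbalance distorts the result by shifting the estimate. The rule uses baseline data and arm, not outcomes, and adjusting for a prognostic variable that is imbalanced by chance corrects the estimate. The defect is only that the model is not fully specified in advance.
- A reader might take E.3 ("Benefits from the BTB and antidepressant medication have been additive") as evidence that a prior fill is strongly prognostic. That sentence concerns treatment benefit in earlier studies, not the prognostic value of a fill in the 90 days before randomization.
- A reader might take E.7.a ("We note that we deliberately consider antidepressant use in our randomization/minimization scheme") to mean that interpretability rests on the minimization. That section rests it on the absence of interaction in earlier studies and merely notes the minimization.

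**Conclusion.** The point holds as a low-severity improvement. The trial minimizes on four factors that it calls prognostic, then does not commit to adjusting for them, and its selection rules exclude them or almost never pick them. The planned standard error is about 0.8 to 12% too large over an assumed R² of .02 to .20. Power lost is about 0.2 to 1.5 points at ρ = 0.5 and 0.2 to 3.5 points at ρ = 0. Mild conservatism is clear only near R² = .20. For IDS-SR the low end is the more likely; the other three primary outcomes may gain more. If the factors are not prognostic, there is nothing to gain.

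The figures rest on assumptions that the documents do not settle: R², ρ, the assignment probability, the 50% splits for age and PHQ-9, and the 70% fill rate. That last figure describes any fill among 2010 patients, not the 90-day minimization variable. N = 330 is unaffected.

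**What to change.** In E.11.b, for the 12- and 24-week regressions of the primary outcomes, pre-specify treatment, baseline outcome, site and the four minimization factors, using the categories and values entered in the minimization program. Keep the unadjusted difference with its interval. Move covariate selection by baseline significance test (E.11.a and E.11.b) to a labelled sensitivity analysis, so that the primary model is fixed before baseline data are compared by arm.

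Two minor drafting points can be settled in the same edit. E.9.d and the E.11.b table should agree on whether provider activity and comorbidities are always in the model or only candidates; which is the sponsor's choice. E.5 takes PHQ-9 severity at the time of baseline measures, while the E.10 schedule shows PHQ-9 only at screening, so the value used should be stated.

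Cost: wording only and no new data. The model spends four degrees of freedom out of about 264 analysed patients (330 × 0.80). If the factors turn out not to be prognostic, the standard error is about 0.2% larger and power about 0.1 point lower.

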Veteran Peer-Assisted Computerized Cognitive Behavioral Therapy for Depression

NCT02057042

September 4, 2019

[figure not shown]
E. RESEARCH APPROACH/METHODS

E.1 Study Design This will be a Hybrid I randomized controlled trial (RCT) of peer-supported cCBT (PS-cCBT) compared to enhanced usual care (EUC) among Veterans with new diagnoses of depression in primary care. Patient assessments will occur at baseline, 12 and 24 weeks following enrollment.

(Study flow of the RCT is shown in Figure 2.)

Concurrent with the RCT, we will collect administrative and qualitative data that will allow us to better understand the context and process of the PS-cCBT implementation including barriers/facilitators to patient recruitment, integration of the peer specialist into the Primary Care-Mental Health Integration team, challenges and successes in maintaining contact with patients, and patient perspectives of peer specialist calls and cCBT content and helpfulness.

Figure 2: Overall Study Flow

Medical Center in Detroit is located in a highly urban area and serves a large number of African American Veterans; whereas, many of the CBOCs from Battle Creek serve rural areas.

During FY 2010, the three study sites (Ann Arbor, Battle Creek, and Detroit) and their associated CBOCs served 6,283 patients who met criteria for a new depressive episode, of which 3,312 were diagnosed with new episode of depression in primary care. Approximately, 11% of these patients were women, 25% were aged 44 or younger, 53% were ages 45-64, and 22% were ages 65 or older. Of patients with known race, 27% were African American. In prior RCTs conducted in several of these study sites, we were successful in recruiting 17% African Americans and 20% women. Thus, we have been quite successful in recruiting women and have also recruited African Americans in proportion to their percentage nationally (18%) of the VA patient population with depression diagnoses.(11)

E.3 Patient Eligibility Criteria

We have deliberately made our inclusion criteria for this study broad and our exclusion criteria narrow to increase the generalizability of our findings to VA primary care patients with new depressive episodes.

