Effects over time: We will next compare the effects of the PS-cCBT intervention versus EUC over time. This second set of analyses will use linear mixed-effects model with outcomes at all three assessment times as the response variable. The mixed-effects model will include patient as random intercepts to take into account the correlation of data within person over time. The model will allow the full use of all observed data despite missing outcomes at one or two assessment times and will give unbiased estimates as long as the missingness does not depend on the unobserved missing data (missing at random).

Using this model, we will be able to estimate the time-averaged effect of the intervention if the response to the intervention is immediate and lasting, or compare the rates of changes in the outcomes between the two groups if the outcomes show different trends between the study groups. Whether we compare the time-averaged effects or the rates between two groups, we will be guided by careful graphical exploration of the longitudinal data over time between the two groups. For example, if we find scores from IDS-SR to slowly decrease over time in the intervention group, but to slightly increase in the enhanced usual care group, we will model this by including a continuous time indicator (e.g., month since randomization) and a time by intervention group term in the model. The coefficient from the interaction term will estimate the difference in rates of change in outcomes between the two study groups.

E.11.c Secondary Outcomes: Analyses of secondary outcome of Depression Coping Skills and antidepressant medication adherence will proceed as outlined above for the primary outcome variables. For analyses of receipt of VA and non-VA traditional in-person psychotherapy, we will compare the percent

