We propose to enroll 330 patients in total (165 per group). The sample size was calculated to provide 90% power to detect a difference in levels of depressive symptoms at the primary end-point of 24 weeks, conservatively assuming a mean effect size of 0.4 SD with a two-tailed alpha of .05 and 20% dropout. We expect that this effect size is conservative based on the meta-analysis completed by Spek et. al. The meta analysis of cCBT interventions for depression and anxiety found that RCTs of cCBTs for depression and anxiety with therapist support had a mean effect size of 1.00 SD, while unsupported cCBT had a mean effect size of 0.26 SD. This suggests that we can reasonably expect our peer-supported cCBT to have an effect size in the range of 0.4 to 0.6 SD compared with enhanced usual care. In another study, Titov et al, reported an effect size of 1.1 from a technician supported cCBT for depression. In our pilot work, congruent with reported effect sizes in the literature in other populations, we found that depressive symptoms among Veterans with depression enrolled in BTB were reduced by 27%, with a mean BDI-II of 21.9 (SD=11.1) at baseline and 16 (SD=13.5) at 8 weeks. Although the pilot study did not have a control group and the endpoint was at 8 weeks, the effect size estimated based on changes from baseline to 8 weeks can be considered to range from 0.43 SD (with an assumed SD of 13.5) to 0.53 SD (an assumed SD of 11.1). Thus, based on the meta-analyses and our pilot data, we consider a between-group difference of 0.4 SD a clinically meaningful and detectable effect size for the proposed intervention. We also note that for the analysis using longitudinally measured data, the power will also depend on the within-person correlation. The proposed sample size, however, will likely give greater power than 90% if 0.4 SD is the time-averaged between-group difference.

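### The over-time mixed model states no covariance beyond a patient random intercept; if correlations fall with time between visits, type I error for the group-by-time term is about 7–10% instead of 5%

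*Combined protocol and SAP*

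**What the plan says.** Section E.11.b has two sets of analyses. The first is a baseline-adjusted regression at each visit, and the plan ranks it: "Comparison at 24 weeks post-enrollment will be our primary comparison". The second is the over-time model: "This second set of analyses will use linear mixed-effects model with outcomes at all three assessment times as the response variable". Section E.1 fixes the visits: "Patient assessments will occur at baseline, 12 and 24 weeks following enrollment". Baseline is therefore one of three equally spaced responses.

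Within-person correlation is handled in one sentence: "The mixed-effects model will include patient as random intercepts to take into account the correlation of data within person over time". No random slope, residual covariance structure, robust standard error or covariance check is stated.

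The over-time model has two possible targets, and plots decide between them. One is an average effect: "we will be able to estimate the time-averaged effect of the intervention if the response to the intervention is immediate and lasting". The other, for diverging trends, adds continuous time and its product with group: "The coefficient from the interaction term will estimate the difference in rates of change in outcomes between the two study groups".

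The plan also says that the model "will give unbiased estimates as long as the missingness does not depend on the unobserved missing data (missing at random".

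Section E.13 reports the pilot's depression scores, "with a mean BDI-II of 21.9 (SD=11.1) at baseline and 16 (SD=13.5) at 8 weeks". It notes that power for the longitudinal analysis depends on within-person correlation, but gives no value for it.

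**The concern.** A random intercept with independent, equal-variance residuals is compound symmetry. Every visit has the same variance, and every pair of visits has the same correlation. In a depression trial, correlation commonly weakens as visits move apart, and patients who improve at different rates produce that pattern. Equal variance at baseline is also open to doubt, because entry requires a PHQ-9 score of at least 10, which can narrow the baseline spread.

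The group-by-time term compares within-person change. Its reported standard error therefore depends on how the model divides variance within patients. If that division is wrong, the confidence interval and p-value for the difference in rates of change are wrong too. The model serves the four primary outcomes named in E.11.b, and E.11.c extends the approach to coping skills and antidepressant adherence.

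**Working it through.** **The plan's own figure.** E.13 gives 0.4 SD, two-sided alpha 0.05, 90% power and 20% dropout. Per arm, n = 2 × (1.960 + 1.282)² / 0.4² = 131.3, so 132. Then 132 / 0.8 = 165 per arm, or 330 in total, with power of 90.1% at 132 evaluable. The figure reproduces and makes no use of the mixed model.

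**Inputs for the group-by-time term.** From the documents: visits at 0, 12 and 24 weeks, and pilot SDs of 11.1 (baseline) and 13.5 (8 weeks). Assumed: all correlations, the pilot's 8-week SD standing for both weeks 12 and 24, BDI-II standing for the IDS-SR, a straight-line mean trend, and complete data.

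**Formulas.** For three equally spaced visits, two orthogonal within-person contrasts are free of the random intercept: linear, L = (y24 − y0)/√2, and quadratic, Q = (y0 − 2·y12 + y24)/√6.

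- VL = [s0² + s24² − 2·c(0,24)] / 2
- VQ = [s0² + 4·s12² + s24² − 4·c(0,12) − 4·c(12,24) + 2·c(0,24)] / 6

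Here c is the covariance of the two visits. The slope difference has true variance proportional to VL. The random-intercept model assumes VL = VQ and so estimates (VL + VQ)/2. Hence:

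- k = true SE / reported SE = √[VL / ((VL + VQ)/2)]
- type I error = 2 × P(Z > 1.96/k)

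**Worked case:** pilot SDs, correlations 0.6 (0–12), 0.7 (12–24), 0.4 (0–24). Variances are 123.21, 182.25 and 182.25; covariances are 89.91, 127.575 and 59.94.

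- VL = (123.21 + 182.25 − 119.88)/2 = 92.79
- VQ = (123.21 + 729 + 182.25 − 359.64 − 510.30 + 119.88)/6 = 47.40
- k = √(92.79/70.095) = 1.151; type I error = 2 × P(Z > 1.703) = 8.8%

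**Other cases, same formulas:**

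| Correlations (0–12 / 12–24 / 0–24) | SDs | k | Type I error |
|---|---|---|---|
| 0.5 / 0.5 / 0.5 | equal | 1.000 | 5.0% |
| 0.6 / 0.6 / 0.5 | equal | 1.074 | 6.8% |
| 0.6 / 0.6 / 0.36 | equal | 1.155 | 9.0% |
| 0.7 / 0.7 / 0.49 | equal | 1.174 | 9.5% |
| 0.5 / 0.5 / 0.5 | pilot | 0.973 | 4.4% |
| 0.5 / 0.65 / 0.4 | pilot | 1.090 | 7.2% |
| 0.6 / 0.7 / 0.5 | pilot | 1.093 | 7.3% |
| 0.6 / 0.7 / 0.4 | pilot | 1.151 | 8.8% |

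**What drives the inflation.** Rerunning the last four rows with equal SDs gives 5.0%, 7.9%, 8.0% and 9.6%. The pilot's rise in variance lowers type I error in every case. Only the falling correlations raise it.

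**With dropout.** Simulated random-intercept fits used 165 per arm and 2,000 runs per scenario, with 10% lost before week 12 and 20% by week 24, completely at random. Rejection rates were 4.2–5.3% under compound symmetry, 6.4–9.1% with falling correlations, and 3.9–5.0% with rising variance alone.

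**Time-averaged target.** A single group effect averaged over the three visits depends on the variance of each patient's mean. With complete data, the random-intercept model estimates that variance directly, so its standard error is right whatever the covariance.

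**Missing at random.** Large-sample checks used about 20% missing at week 24, depending on the observed week-12 score. With the same rule in both arms, the slope difference was off by at most 0.03 points per 12 weeks. With opposite rules by arm (pilot SDs, 0.6/0.7/0.4, no true effect), the random-intercept model gave a false 24-week difference of about 0.45 points, or 0.45/13.5 = 0.03 SD. The correct covariance gave about zero.

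**The case against.** The best defence is that the text does not confine the model to a random intercept. It says that the intercept is included and leaves the residual structure open, so an analyst could add one without breaking the plan. This stands. The defect is under-specification, with compound symmetry as the default.

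A second point is that the documents contain no evidence of inflated error. A reader might take the pilot SDs as proof that the standard error is too small. They are not: a variance rise alone makes the test slightly conservative. The pilot also used another scale, stopped at 8 weeks, had no control group and, according to E.7.c, included specialty mental health patients. It cannot settle the covariance in this trial. This stands too.

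Third, the difference in rates is only one of the two targets and is used if plots show diverging trends. The model is also not the primary comparison. Both are correct and limit the consequence.

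None of this supplies the missing specification. E.11.b presents effects over time as one of two broad types of analysis for the primary aims, and nothing in the plan supports equal correlations.

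**Conclusion.** The point holds as a minor, conditional one. The stated model implies equal variances and equal correlations unless the analyst adds something that the plan does not mention. In the falling-correlation cases checked, the true standard error of the group-by-time term is 1.07 to 1.18 times the reported one, and type I error is about 7–10%. Milder decay gives less, and compound symmetry gives exactly 5%. The correlations and the week-12 and week-24 SDs are assumptions.

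Two stronger readings are not supported. One is that the standard errors are wrong, or usually too small: they may be right, too small or slightly too large, and the documents do not give the correlations needed to tell. The other is that the trial's main result is at risk: the 24-week regression and the 330-patient calculation do not use this model.

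The time-averaged effect is safe with complete data when it is a single group effect over the three visits; the plan does not give its coding. The missing-at-random statement leaves out a condition, a correct covariance, but the bias found was small.

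**What to change.** In E.11.b, for the over-time model, replace the random-intercept covariance with an unstructured covariance over baseline, 12 and 24 weeks, with Kenward-Roger degrees of freedom. Keep the planned time-averaged or rate contrast, and state that the baseline-adjusted regression remains the primary 24-week estimate, so that the two models do not give competing answers. Add to the missing-at-random sentence that it also relies on a correctly specified covariance.

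The unstructured covariance remains valid if compound symmetry holds. It has six covariance parameters instead of two, so four more, which is little with 330 patients and three visits. The change takes a line or two of text and needs no new data or patients.
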